9.8. TREATMENT COMPLIANCE

Treatment compliance will be assessed based on drug accountability and review of the subject diary. Subjects/parents/legal guardians/caregivers will be instructed to return all empty investigational product vials and/or DCCs at all study visits after Visit 1. The completed subject diary, which captures the date, time, person administering investigational product, injection site and dose of investigational product, should be returned at each site visit. All investigational product, used and unused, shall be returned at the end of the subject's participation in the trial or at the visit following investigational product discontinuation.

9.9. PRIOR AND CONCOMITANT THERAPIES

9.9.1. Prior Therapy

Prior therapy taken during the prior trial will be captured and recorded.

9.9.1.1. Previous hGH Therapies

Subjects who were treated with Genotropin in the prior TransCon hGH CT-301 trial should be instructed NOT to take their regular dose of Genotropin on the day of Visit 1.

9.9.2. Permitted and Prohibited Therapies

Concomitant therapy is considered any medication other than the investigational product that is administered from the first dose of investigational product administration up until the end of the trial. Any change in documented, permitted concomitant medication must be recorded in the eCRF, noting the type of medication, the dose, start date, stop date (if applicable), and indication. If the administration of a prohibited concomitant medication becomes necessary, participation in the trial may be discontinued prematurely for that subject, based on a decision made jointly by the investigator and Medical Expert.

9.9.2.1. Permitted Therapies

1. Replacement therapy for other non-GH pituitary deficiencies. As hGH may enhance the transformation of hydrocortisone to cortisone, the investigator may increase the dose of hydrocortisone replacement therapy if needed (eg, for anticipated stress).
2. Treatment for diabetes
3. Over-the-counter vitamins, minerals, or other dietary supplements only if their use is agreed to by the investigator.

9.9.2.2. Prohibited Therapies

1. Weight-reducing drugs or appetite suppressants, unless used for management of attention-deficit/hyperactivity disorder (ADHD)
2. hGH therapies other than TransCon hGH

10. TRIAL PROCEDURES

10.1. TRIAL DURATION

Each subject's participation is expected to last up until:

- the product is approved and commercially available,
- alternative arrangements have been made for continued subject access to hGH treatment, or
- treatment for pediatric growth hormone deficiency is no longer considered appropriate (including—but not limited to—when there is evidence of closed epiphyses [bone age >14.0 years for females; > 16.0 years for males]).

When any of the 3 criteria is met, the subject will be considered to have completed the extension trial. The total duration of participation for each subject in the trial will therefore depend on the conditions listed above and may be different in different countries and regions.

10.2. TRIAL PERIODS AND VISITS

Following confirmation of eligibility, enrolled subjects will begin attending morning visits every 13 weeks (± 2 weeks):

- **Visit 1:** Week 1 (Day 1 is the 1st weekly dose)
- **Visit 2:** Week 13 (± 2 weeks), 5 days (± 1 day) after the 11th, 12th, 13th, 14th or 15th dose
- **Visit 3:** Week 26 (± 2 weeks), 5 days (± 1 day) after the 24th, 25th, 26th, 27th or 28th dose

This pattern will continue until completion of the trial. All visits should be in the morning for consistent height measurements. Attempts should be made to adhere to the planned visit schedule. It is suggested that the site staff provide dosing, diary, and visit reminders (eg, phone calls) to subjects/parents/legal guardians/caregivers between visits, especially for those subjects who transitioned from Genotropin to TransCon hGH.

An overview of all visits is provided in the Schedule of Events (Section 18.2).

For detailed descriptions of assessments refer to Section 11.

10.2.1. Visit 1 and Day 1

Prior to any protocol related activities or evaluations, informed consent will be obtained from each potential subject in accordance with GCP and regional regulatory requirements. Informed consent may be obtained during the prior trial. The format and content of the ICF must be approved by the appropriate IRB/HREC/IEC prior to implementation. Release of medical information authorization should also be obtained at the time of informed consent.

Visit 1 of the extension trial should be the same day as the final visit of the prior trial and may occur over several days. To continue uninterrupted treatment with hGH, Day 1 (the first weekly dose) should occur on the day of Visit 1 if the subject is entering after completion of the TransCon hGH CT-301 trial (heiGHt trial), or as soon as possible thereafter. If the subject is entering after completion of the TransCon hGH CT-302 (fliGHt trial), they should remain on their dosing schedule and take their dose approximately two days after Visit 1, or as soon as possible thereafter. To accommodate extension trial activities and scheduling of procedures, the weekly dosing and visit schedule may need to be adjusted as a subject enters the extension trial. In unusual situations, a period of up to approximately 6 weeks between the final visit of the prior trial and the first dose of the extension trial is acceptable.

During Visit 1 (and again on Day 1, if on a subsequent day), the investigator will review all baseline data collected to determine the subject's eligibility. Data collected up through the final visit of the prior trial may be used as baseline data for the extension trial. The following will be performed for Visit 1 of the extension trial:

1. Medications and health status review

- Medical history from the prior trial will be carried forward into this trial

-
- Ongoing AEs from the prior trial will be followed until resolution or stabilization
 - Review of subject diary from the prior trial
 - Current therapies
 - Interval history since last visit of prior trial
2. Vital sign measurements
 3. Height and weight measurements
 4. Physical examination
 - Local tolerability assessment. **For subjects who were treated with Genotropin in the prior TransCon hGH CT-301 trial**, Visit 1 injection site examinations to the daily hGH treatment areas should be explicitly documented so as to differentiate from any new reactions that occur during the extension trial.
 5. Pubertal status assessment (Tanner stage, including onset of menses)
 6. Blood collection for the following laboratory assessments*:
 - IGF-1 and IGFBP-3
 - Antibodies against hGH and PEG
 - These analyses may only be conducted after enrollment and are not required for eligibility verification. These data will be used to support evaluation of post-dose antibody detection
 - If warranted, TransCon hGH, hGH, and PEG serum levels may be analyzed for the interpretation of immunogenicity titers
 - mPEG
 - Hormone/glycemic status (TSH, FT4, FT3, morning cortisol, and HbA1c)
 - Chemistry
 - Hematology
 - Lipid panel
 - **Females of child-bearing potential only:** hCG
- *Fasting not required. Banked blood samples may be used for additional characterization of anti-drug antibody responses.
7. Bone age x-ray
 - A bone age x-ray performed within approximately the past 52 weeks may be acceptable with appropriate documentation. However, if the last recorded bone age was > 12.0 years, and the bone age x-ray was performed greater than 9 months prior to Visit 1, a bone age x-ray should be performed within approximately 4 weeks of Visit 1.

8. Investigational product preparation/administration training/re-training

- May also be performed at other visits, as needed
- Includes review of the TransCon hGH Instructions for Use (also provided to the subject/parent/legal guardian/caregiver for reference throughout the trial)
- When the GH Auto-Injector is available, thorough onsite training of investigational product preparation and administration will occur at the earliest regularly scheduled visit (including the 1st visit upon transition of the GH Auto-Injector in the US where the GH Auto-Injector will be used.
- Includes instructions that administration of investigational product should occur at approximately the same time of day on the same day of the week throughout the trial. Details regarding adjustment of a subject's established dose day/time are provided in the trial manual.

9. Subject diary completion review, as needed

- May also be performed at other visits, as needed
- Includes reminder to complete Week 6 PRO questionnaires prior to 6th dose of investigational product
- In those subjects using the GH Auto-Injector: includes reminder to complete the Device Usability Questionnaire (DUQ) on the day of 6th dose using the GH Auto-Injector

10. Patient-reported outcome questionnaires

- Convenience and Overall Satisfaction domains (C&OS) of the Treatment and Satisfaction Questionnaire for Medication (TSQM-9)
 - For the parent (C&OS-P)
- Child Sheehan Disability Scale
 - For the parent (CSDS-P)
 - **For the child ≥ 9 years old only:** (CSDS-C)

11. Investigational product dose adjustment (from prior trial), as needed

- Investigational product volume is based on weight measurement obtained at Visit 1 and the Bracketed Weight Table for TransCon hGH, or the GH Auto-Injector dosing table

12. Investigational product and subject diary dispensing

In the unusual event there is a gap of 4 to approximately 6 weeks between the assessments done for Visit 1 and Day 1 (first dose), then all of the above should be repeated except physical exam, blood collection, and bone age x-ray.

Following Visit 1, TransCon hGH will be administered by subject/parent/legal guardian/caregiver as a once weekly SC injection. Once weekly healthcare services may be offered for the first 4 weeks of a new treatment (eg, subjects beginning TransCon hGH in this trial) to accommodate home administration of TransCon hGH. Extended support may be offered until subjects/parents/legal guardians/caregivers are comfortable assuming responsibility for

administration of the investigational product. See Section 9.3 for details regarding TransCon hGH administration and Section 9.6 for details regarding dose adjustments.

10.2.2. Week 6, Visit 2 and scheduled visits every 13 weeks ongoing

- For subjects who were treated with Genotropin in the TransCon hGH CT-301 trial, immediately prior to the 6th investigational product administration (Week 6), patient-reported outcome questionnaires within the subject diary will be completed
- Visit 2 and subsequent scheduled visits every 13 weeks (± 2 weeks) will be performed 5 days (± 1 day) post-dose

Subjects should adhere to the planned visit schedule. It is suggested that site staff provide dosing, diary, and visit reminders (eg, phone calls) to subjects/parents/legal guardians/caregivers between the visits, especially for those subjects who transitioned from Genotropin to TransCon hGH and for those that transitioned from vial and syringe to the GH Auto-Injector.

10.2.2.1. Patient-Reported Outcome Completion (Week 6 within Diary; Visit 2 at Clinic Visit)

For subjects who were treated with Genotropin in the prior TransCon hGH CT-301 trial: Between Visit 1 and Visit 2, immediately prior to the 6th investigational product administration and at Visit 2, the following patient-reported outcome questionnaires will be completed by subjects/parents/legal guardians/caregivers, as applicable. At Week 6, the questionnaires will be completed in the subject diary. At Visit 2, the questionnaires will be completed at the clinic visit, prior to review of the subject diary, AEs, and concomitant medications.

- PQ-P
- PQ-C: **only for subjects ≥ 9 years old (at Visit 1)**
- C&OS-P
- CSDS-P
- CSDS-C: **only for subjects ≥ 9 years old (at Visit 1)**

10.2.2.2. Visit 2, Visit 4, Visit 6 and every 6 months ongoing (even-numbered visits)

The following assessments will be performed at Visit 2, Visit 4, Visit 6, and every 6 months ongoing (even-numbered visits):

1. Concomitant medications
 - Includes review of subject diary
2. AE review
 - Includes review of subject diary
3. Investigational product compliance calculation
 - Includes review of subject diary and returned investigational product
4. Vital sign measurements

5. Height and weight measurements
 6. Physical examination
 7. Pubertal status assessment (Tanner stage)
 8. Blood collection for the following laboratory assessments*:
 - IGF-1 and IGFBP-3
 - Antibodies against hGH and PEG
 - If warranted, TransCon hGH, hGH, and PEG serum levels may be analyzed for the interpretation of immunogenicity titers
 - Females of child-bearing potential only: hCG
- *Banked blood samples may be used for additional characterization of anti-drug antibody responses

9. Investigational product dose adjustment, as needed
10. Investigational product and subject diary dispensing

An overview of all visits is provided in Section 18.2.

10.2.2.3. Visit 3, Visit 5, Visit 7 and every 6 months ongoing (odd-numbered visits)

The following assessments will be performed at Visit 3, Visit 5, Visit 7, and every 6 months ongoing (odd-numbered visits), unless otherwise indicated:

1. Concomitant medications
 - Includes review of subject diary
2. AE review
 - Includes review of subject diary
3. Investigational product compliance calculation
 - Includes review of subject diary and returned investigational product
4. Vital sign measurements
5. Height and weight measurements
6. Physical examination
7. Pubertal status assessment (Tanner stage)
8. Blood collection for the following laboratory assessments*:
 - IGF-1 and IGFBP-3
 - Antibodies against hGH and PEG
 - If warranted, TransCon hGH, hGH, and PEG serum levels may be analyzed for the interpretation of immunogenicity titers
 - mPEG

- Hormone/glycemic Status (TSH, FT4, FT3, morning cortisol, and HbA1c)
- Chemistry
- Hematology
- Lipid panel
- **Females of child-bearing potential only:** hCG
*Fasting not required. Banked blood samples may be used for additional characterization of anti-drug antibody responses.

9. Investigational product dose adjustment, as needed

10. Investigational product & subject diary dispensing

An overview of all visits is provided in the Schedule of Events, Section 18.2.

10.2.2.4. Patient-Reported Outcome Completion (6th week after transition to the GH Auto-Injector) and Device Usability Questionnaire

For all subjects who have transitioned to the GH Auto-Injector (6th week of GH Auto-Injector Use): Immediately prior to the 6th dose of the GH Auto-Injector, and at the next scheduled clinic visit (approximately 13 weeks after transition to the GH Auto-Injector), patient-reported outcomes questionnaires will be completed by subjects/parents/legal guardians/caregivers, as applicable. At 6 weeks after transition to the GH Auto-Injector, the questionnaires will be completed in the subject diary. At the next scheduled clinic visit (approximately 13 weeks after transition to the GH Auto-Injector), the questionnaires will be completed at the clinic visit, prior to review of the subject diary, AEs, and concomitant medications. The questionnaires are:

- C&OS-P
- CSDS-P
- **CSDS-C: only for subjects ≥ 9 years old (at time of transition to GH Auto-Injector)**

In addition, on the day of the 6th dose using the GH Auto-Injector (either immediately before or after the 6th dose) and at the next scheduled clinic visit (approximately 13 weeks after transition to GH Auto-Injector), the following questionnaire will be completed by the individual primarily responsible for preparing and performing the injection with the GH Auto-Injector.

- DUQ

10.2.2.5. GH Auto-Injector Data Read-Out

After approximately 3 to 6 months of subjects being on the auto-injector, there is a potential that new devices may be shipped to the sites so that the subject may exchange their device and receive a new one. The used devices may be sent to Ascendis for data download and analysis, which will include no clinical or personal data. The device serial number may be logged to the subject's study ID, but not any patient identifiers.

The potential data collected by the device are as follows:

1. Injection Log

- A log entry of this type is stored after each successful injection.

2. Other Data Log

- Timestamp
- Dose size

3. Other information

- Charge time
- Battery level
- Motor stop position
- Position of first rubber stopper (used cartridge detect)

4. Errors Log

An error log entry will contain the data:

- Timestamp
- Error code (eg “self-test error” or “injection user abort”)
- Additional error information that depends on the “error code”

5. Reset Log

If a reset occurs, it is logged.

- Timestamp
- Reset cause (eg “watchdog” or “software”)
- Additional reset information

10.2.2.6. Annual Assessments

The following will be performed annually (Visit 5, Visit 9, etc.) and/or anytime if clinically indicated

- Bone age x-ray

10.2.3. Unscheduled Visits

Unscheduled visits are those visits that occur between regularly scheduled visits and are performed to assess a previously noted AE, abnormal laboratory value(s), and/or clinical findings. In such cases, the subject/parent/legal guardian/caregiver will be contacted to arrange an unscheduled visit. Only focused assessments (guided by the reason for the visit) will occur at these visits.

10.2.4. Completion/Early Termination Visits

If treatment is permanently discontinued for any reason, trial participation will be discontinued and a Completion Visit/Early Termination Visit (procedures indicated for Visit 5 in the Schedule of Events table, as applicable) will be performed. Completion of the trial is described in Section 10.1. Early termination is when a subject's trial participation discontinues prior to completion of the trial.

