8.2. PREMATURE SUBJECT WITHDRAWAL

Early withdrawal occurs when an enrolled subject ceases participation in the trial, regardless of the circumstances, prior to the expected completion of the trial, which in this study is until a) the product is approved and commercially available, b) the Sponsor makes alternative arrangements for continued subject access to hGH treatment, or c) treatment for pediatric growth hormone deficiency is no longer considered appropriate. Additionally, the investigator may discontinue the treatment of a subject at any time if considered to be in the subject's best interest. If treatment is permanently discontinued for any reason, trial participation should be discontinued. If the subject completes the trial or discontinues prematurely, a Completion Visit/Early Termination Visit should be performed. See Section 7.3.1 for a list of valid reasons for early termination of subjects from the trial.

For trial discontinuations, the investigator should schedule a Completion Visit/Early Termination Visit to collect data, particularly AE data reported up to 14 days after the final dose of TransCon hGH (if applicable), and to collect blood for laboratory evaluations. This visit should contain all assessments from Visit 5 (Week 52, see Schedule of Events, Section 18.2), as applicable, and will be documented in the eCRF together with the reason(s) for trial discontinuation.

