11.7.1. Preference Questionnaire

The Preference Questionnaire should only be completed for subjects who were treated with daily Genotropin in the prior TransCon hGH CT-301 trial. The parent/legal guardian/caregiver will complete the PQ-P, while the subject, if ≥ 9 years old at Visit 1, will complete the PQ-C.

The timing of the preference questionnaires is listed in [Section 10.2.2.1](#).

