18.2. SCHEDULE OF EVENTS

	VISIT 1 ¹	VISIT 2	VISIT 3	VISIT 4	VISIT 5/CV/ETV ²
	Week 1 Day 1	Week 13 (± 2 weeks)	Week 26 (± 2 weeks)	Week 39 (± 2 weeks)	Week 52 (± 2 weeks)
	Morning	5d ± 1d Post-Dose, Morning	5d ± 1d Post-Dose, Morning	5d ± 1d Post-Dose, Morning	5d ± 1d Post-Dose, Morning
Informed consent	x				
Interval history, medications and health status review ³	x				
Vital signs measurements ⁴	x	x	x	x	x
Height ⁵ & weight	x	x	x	x	x
Physical examination	x	x	x	x	x
Pubertal status assessment	x	x	x	x	x
Blood sample collection – A ⁶	x	x	x	x	x
Blood sample collection – B ⁷	x		x		x
Bone age x-ray ⁸	x				x
Investigational product preparation/administration training	x				
Training on GH Auto-Injector ⁹	(x)	(x)	(x)	(x)	(x)
Subject diary training	x				
C&OS-P ¹¹	x ¹⁰	x			
CSDS-P ¹¹	x ¹⁰	x			
CSDS-C ^{11,12}	x ¹⁰	x			
PQ-P ¹¹		x			
PQ-C ^{11,12}		x			
DUQ ¹¹		x			
Investigational product dose adjustment ¹³	x	x	x	x	x
Local tolerability assessment ¹⁴	x	x	x	x	x
Investigational product & subject diary dispensing	x	x	x	x	x
Investigational product compliance ¹⁵		x	x	x	x
Concomitant medications		x	x	x	x
Adverse events ¹⁶		x	x	x	x

- ¹ Visit 1 of this extension trial should be the same day as the final visit of the prior trial, and the first dose should occur as soon as possible. A period of up to approximately 6 weeks between the final visit of the prior trial and first dose (Day 1) of the extension trial is acceptable. Visit 1 assessments should be performed unless they were performed for the final visit of the prior trial. In the unusual event there is a gap of 4 to approximately 6 weeks, then all Visit 1 assessments should be repeated for Day 1 except physical exam, blood collection and bone age x-ray.
- ² After Visit 5, visits continue every 3 months (See Section 10.2.2.3 and Section 10.2.2.5). A Completion Visit (CV)/Early Termination Visit (ETV) should be performed for all subjects either completing the trial as described in Section 10.1, or terminating trial participation prematurely. The visit should include all procedures listed for Visit 5, as applicable.

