- ¹¹ For subjects who were treated with Genotropin in the prior TransCon hGH CT-301 trial, C&OS-P, CSDS-P, CSDS-C, PQ-P, and PQ-C will be completed (as applicable) within the subject diary immediately prior to the 6th dose of investigational product, and in clinic at Visit 2, prior to review of the subject diary, AEs, and concomitant medications. For subjects transitioning to the GH Auto-Injector, C&OS-P, CSDS-P, and CSDS-C will be completed (as applicable) within the subject diary immediately prior to the 6th dose after transition to the GH Auto-Injector, and again in clinic at the following scheduled visit, prior to review of the subject diary, AEs, and concomitant medications. Additionally, for subjects transitioning to the GH Auto-Injector, the DUQ will be completed within the subject diary on the day of the 6th dose of investigational product, and in clinic at Visit 2, prior to review of the subject diary, AEs, and concomitant medications.
- ¹² CSDS-C and PQ-C should only be completed by subjects \geq 9 years old at the time of Visit 1, and/or at the transition to the GH Auto-Injector, as applicable.
- ¹³ Dose adjustments at visits are typically based on subject weight at visits. However, dose adjustments may occur between visits per Section 9.6.
- ¹⁴ Local tolerability assessment at the injection site to be performed at time of injection, and by the trial staff at visits.
- ¹⁵ Investigational product compliance includes review of subject diary and returned investigational product.
- ¹⁶ AE review includes review of subject diary and physical examination of injection sites. AEs that are considered mild and not related to investigational product will not be reported on the AE CRF. AEs reported up to 14 days after the final dose of TransCon hGH will be captured.

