11.1. Preference Questionnaire

The Preference Questionnaire should only be completed for subjects who were treated with daily Genotropin in the prior TransCon hGH CT-301 trial. The parent/legal guardian/caregiver will complete the PQ-P, while the subject, if \geq 9 years old at Visit 1, will complete the PQ-C.

The frequency and percentages will be summarized for each question for PQ-P and PQ-C in tables. Listings will also be provided for PQ-P and PQ-C.

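### Preference and satisfaction questionnaires are not scheduled at the Early Termination Visit, so ex-Genotropin subjects who leave before Visit 2 have no Visit 2 answer

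*Protocol*

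**What the plan says.** Preference for weekly or daily treatment and satisfaction with treatment over time are secondary objectives (Protocol 6.2, SAP 2.2). The corresponding endpoints are listed as other endpoints (Protocol 14.1.4, SAP 3.3.4).

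**Who is asked, and when.** Protocol 11.7.1: "The Preference Questionnaire should only be completed for subjects who were treated with daily Genotropin in the prior TransCon hGH CT-301 trial". Note 11 of the Schedule of Events has these subjects complete the PQ, C&OS-P and CSDS "within the subject diary immediately prior to the 6th dose of investigational product, and in clinic at Visit 2". Protocol 10.2.2.1 agrees: "At Week 6, the questionnaires will be completed in the subject diary". The child form (PQ-C) is only for those aged 9 or older at Visit 1.

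**What happens at early termination.** Protocol 10.2.4, on permanent discontinuation: a "Completion Visit/Early Termination Visit (procedures indicated for Visit 5 in the Schedule of Events table, as applicable) will be performed". Protocol 8.2: "This visit should contain all assessments from Visit 5 (Week 52, see Schedule of Events, Section 18.2), as applicable". Note 2 of the Schedule: "The visit should include all procedures listed for Visit 5, as applicable". The Visit 5/CV/ETV column marks none of these questionnaires. Permanent discontinuation ends participation (8.2), and there is no later visit except to follow related serious adverse events (10.2.5).

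**Analysis.** SAP 11.1: "The frequency and percentages will be summarized for each question for PQ-P and PQ-C in tables". It names no time point, denominator or rule for a missing form. By default, SAP section 5 bases percentages on the whole cohort. SAP 5.3 and Table 2 would map a termination visit on Day 2 to 135 to Visit 2.

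**The concern.** The analysis has a Visit 2 slot for an early leaver, but no questionnaire is scheduled to fill it. The families lost this way may not be a random subset. Protocol 9.9.2.2 prohibits hGH other than TransCon hGH, so a family that wants daily injections back can get them, within the plan's rules, only by leaving. Preferring weekly gives no such reason to leave. Missingness may therefore depend on the answer being measured.

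At stake is how far the Visit 2 preference percentages and satisfaction scores can be taken to describe everyone who switched, rather than those who stayed about 13 weeks. The trial is open-label and has no concurrent daily arm, so these answers are its only evidence on preference.

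**Working it through.** **Plan's own figure.** There is no power calculation. The planned number, up to about 300, matches the two prior trials in Protocol 5.3: 150 + 150 = 300. Nothing below depends on it.

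**What is lost**

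| Time of leaving | Week 6 PQ and C&OS-P | Visit 2 PQ and C&OS-P |
|---|---|---|
| Before dose 6 | none | none |
| Between dose 6 and Visit 2 | in diary | none |
| After Visit 2 | in diary | yes |

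A subject who leaves before dose 6 still has the Visit 1 C&OS-P, but that was completed before any weekly dose. The words 'as applicable' can shorten the Visit 5 list; they do not add items to it.

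**Inputs.** Switchers: 150 × 1/3 = 50, from the 2:1 allocation in CT-301. This is a ceiling, since not all need roll over. Assumptions, because the documents give no figures: k = 1, 2, 3 or 5 of 50 leave before Visit 2; p = 10% of those reaching Visit 2 prefer daily; q, the share of leavers preferring daily, runs from 0 to 100%. 'No preference' is ignored. Let f = k/50.

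**Respondents as denominator.** Reported daily share is p; the full-cohort share is (1 − f)p + fq. Error = f(p − q), in percentage points:

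| Leavers | q = 0 | q = 10% | q = 50% | q = 100% |
|---|---|---|---|---|
| 1 of 50 | +0.2 | 0 | −0.8 | −1.8 |
| 2 of 50 | +0.4 | 0 | −1.6 | −3.6 |
| 3 of 50 | +0.6 | 0 | −2.4 | −5.4 |
| 5 of 50 | +1.0 | 0 | −4.0 | −9.0 |

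The understatement cannot exceed f, which is 1/50 = 2 points per leaver.

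**SAP default (whole cohort) as denominator.** The daily share is low by fq and the weekly share is low by f(1 − q). The weekly-minus-daily gap is therefore off by f(2q − 1), which favours weekly only if q exceeds 50%. With 2 leavers the reported gap is 0.96 × (90 − 10) = 76.8 points. The full-cohort gap is 80.8 if no leaver prefers daily, 76.8 if half do and 72.8 if all do.

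**Illustration in whole subjects.** Suppose 5 of 50 leave and all would choose daily, while the other 45 answer 38 weekly, 3 daily and 4 no preference.

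| | Respondents | SAP default | Full cohort |
|---|---|---|---|
| Daily | 3/45 = 6.7% | 3/50 = 6.0% | 8/50 = 16% |
| Weekly | 38/45 = 84.4% | 38/50 = 76% | 38/50 = 76% |

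The weekly overstatement appears only with the respondent denominator.

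**Satisfaction.** The C&OS-P scores run from 0 to 100 and are summarised over non-missing values. With 2 of 50 leaving, an assumed 10-point difference between stayers and leavers would shift the mean by 0.04 × 10 = 0.4 points.

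**The case against.** A reader might infer that the plan understates preference for daily treatment and so favours the sponsor's product. The documents do not support that as a statement of fact. They contain no data on departures before Visit 2 or on leavers' preferences. Families also leave through loss to follow-up or for medical or logistical reasons. The error is zero if leavers resemble stayers and reverses among respondents if they prefer daily less. These families also completed CT-301 and chose to continue, so few may leave early.

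Other counterarguments carry weight. Week 6 diary answers exist for anyone who reached dose 6, so only earlier leavers are lost entirely. Under the SAP's default denominator leavers pull down both shares. Disposition with withdrawal reasons will be tabulated (SAP 6.1), and summaries are planned by prior-treatment group, so a reader could partly bound the effect. The outcome is descriptive and no test depends on it.

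The PQ also asks about injections being taken at present, which fits poorly once treatment has stopped. An answer after one or two doses is not equivalent to one after 13 weeks. Subjects lost to follow-up will attend no termination visit.

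All of this limits the size and certainty of the effect and shapes the remedy. It does not close the gap: the questions are not scheduled at a visit the plan already requires, and SAP 11.1 does not say which answers enter its table or over what denominator.

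**Conclusion.** The gap is certain from the text: no PQ or C&OS-P is scheduled at early termination, and there is no later opportunity to ask. Its effect is conditional. If leavers favour daily more than stayers do, the daily share among respondents is too low by at most about 2 percentage points per leaver; if they do not differ, it is unbiased. Under the whole-cohort default, both shares fall, and the gap favours weekly only when more than half of the leavers prefer daily.

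The 2-point figure assumes about 50 switchers. With fewer it rises: 40, for example, would give 1/40 = 2.5 points. It is also larger for the PQ-C, whose base is restricted by age to a number the documents do not give. No alpha or power is affected. This is a low-cost improvement to a descriptive secondary objective, not a flaw in the trial's main conclusions.

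**What to change.** **Protocol 8.2, 10.2.4 and Schedule of Events notes 2 and 11.** Ex-Genotropin subjects who terminate after at least one TransCon hGH dose and before Visit 2 complete PQ-P, PQ-C (if aged 9 or older at Visit 1) and C&OS-P at the termination visit, before adverse event review. Add an instruction that the form's reference to current injections means the weekly injections taken in this study. The CSDS can stay as scheduled, since it measures treatment burden rather than preference.

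**SAP 11.1.**
- Report the PQ at Week 6 and at Visit 2 as separate time points, with termination answers mapped to Visit 2 under Table 2. Table 2 has no Week 6 row, so Week 6 must be named.
- State the denominator.
- Also show termination answers separately, because exposure is shorter.
- Add a two-way bound counting leavers with no answer as all weekly and as all daily, using Week 6 answers where they exist. If none of the leavers has an answer, p = 10% gives a daily share of 9.6% to 13.6% with 2 of 50 leaving, and 9.0% to 19.0% with 5.

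**Cost.** Amendment wording, forms that already exist at a visit already required, and a few table rows. The downsides are minor family burden, mixed exposure lengths in the Visit 2 row, and possibly a slightly less favourable preference figure.
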